### 2. List of Abbreviations and Definitions of Terms

Abbreviation	Definition
AE	Adverse Event
CE	Conformité Européene
CIP	Clinical Investigation Plan
EU MDR	European Medical Device Regulation
ISO	International Organization for Standardization
SAP	Statistical Analysis Plan

### 3. Introduction

Medtronic, Inc. is sponsoring the Novapak Nasal Sinus Packing and Stent Study, a prospective, observational, multi-site, non-controlled, non-randomized, case-series, investigational, clinical study. The purpose of this study is to assess the safety of the Novapak Nasal Sinus Packing and Stent device used as indicated post-operatively in patients undergoing nasal/sinus surgery. In addition, this study will observe some key measures of device effectiveness from the physician and subject perspective.

The Novapak Nasal Sinus Packing and Stent study is being conducted as a non-significant risk postmarket investigational study in the US and Canada in accordance with Canadian local regulations and International Organization for Standardization (ISO) 14155:2020 in support of European Medical Device Regulation (EU MDR) regulatory submission for a Conformité Européene (CE) Mark.

The Novapak prospective observational clinical trial clinical investigation plan (CIP) provides the guidelines for this statistical analysis plan (SAP). The purpose of this SAP is to provide details for Novapak therapy-specific data analyses. Reports generated using study data may not contain all the analyses described below; however, if a report contains an objective outlined within this document, the analysis of that objective will be performed as described in this SAP. If additional analyses are required but not covered in this SAP, a separate SAP addendum may be needed.

## 4. Study Objectives

## 4.1 Primary Objective

The primary objective of this study is to assess the safety profile of the Novapak Nasal Sinus Packing and Stent device used as indicated post-operatively in patients undergoing nasal/sinus surgery.

Version 1.0

Medtronic

### 4.2 Secondary Objectives

The secondary objectives of this study will gather data to support the effectiveness of Novapak's inherent features and claims of performance:

Adhesions – Sinus packing devices act as a space occupying stent to prevent raw tissues from contact and forming unwanted, obstructive tissue connections known as synechia or adhesions. This study will collect the number of adhesions observed by endoscopic examination as well as a grade of the adhesions based on the percentage of vertical height of the middle turbinate taken up by the adhesion. This data will be compared to historical data related to adhesions post sinus surgery.

**Control of bleeding** – Sinus packing devices control bleeding by absorption and pressure on the bleeding surfaces known as the tamponade effect. Chitosan a component of Novapak also has hemostatic properties. This study will collect data related to post-operative bleeding. Since bleeding can be different for each subject and based on the extent of tissue trauma; a baseline observation immediately post-surgery using the Boezaart Surgical Field Grading Scale will be collected. After the packing is applied the surgical field will be graded again. In addition, any residual bleeding will be observed and noted at the subject visits.

Aid in healing – Novapak acts as an adjunct to aid in the natural healing process by providing a moist environment for the tissues during the proliferation phase of wound healing. In addition, the chitosan component within Novapak has hemostatic properties and is antibacterial to reduce unwanted microbial action which could lead to inflammation. The physician will grade the sinuses before surgery and then at each subject visit using the Lund-Kennedy scoring system. In addition, the subjects will provide sinus health responses to the SNOT-22 questionnaire prior to surgery and again at each subject visit.

## 5. Investigation Plan

Prospective, observational, multi-site, non-controlled, non-randomized, case-series, with adult subjects undergoing nasal/sinus surgery and using Novapak Nasal Sinus Packing and Stent device used as indicated post-operatively with 14-day and 30-day follow-up visits. The study is expected to be conducted at up to 5 study sites located in the US and/or Canada. A minimum of 75 subjects will be enrolled in the study and one device is expected to be used per subject. Study sites that enroll faster than others will be allowed to do so in order to maintain an adequate enrollment rate; however, there is a site maximum enrollment of 60% (45 subjects) of the total enrollment. No known factors have been foreseen that may compromise the outcome of the clinical study or interpretation of the results.

## 6. Determination of Sample Size

As this is not a powered hypothesis-driven study, the sample size of a minimum of 75 subjects was selected that is adequate to assess the safety and treatment effectiveness of the Medtronic Novapak Nasal Sinus Packing and Stent device, not determined by statistical methods.

## Novapak Prospective Observational Clinical Trial Statistical Analysis Plan

Form

Version 1.0

### 7. Statistical Methods

### 7.1 Study Subjects

### 7.1.1 Disposition of Subjects

Disposition of subjects will be summarized by site, product model used, follow-up visit, etc., by flow chart, table, and/or listing.

### 7.1.2 Clinical Investigation Plan (CIP) Deviations

If applicable, protocol deviations will be summarized by deviation type with deviation and subject counts.

### 7.1.3 Analysis Sets

The analysis population will include all patients that fulfill inclusion and exclusion criteria and use the Novapak Nasal Sinus Packing and Stent device in their nasal/sinus surgery.

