Medtronic is responsible for analyzing deviations, assessing their significance, and identifying any additional corrective and/or preventive actions (e.g. amend the CIP, conduct additional training, terminate the investigation). Repetitive or serious investigator compliance issues may result in initiation of a corrective action plan with the investigator and study site, and in some cases, may necessitate suspending enrollment until the problem is resolved or ultimately terminating the investigator's participation in the study. Medtronic will provide study site-specific reports to investigators summarizing information on deviations that occurred at the investigational study site as needed.

Examples of study deviations include but are not limited to:

- Failure to obtain proper IC
- Failure to collect required study data
- Inclusion/exclusion criteria not met
- Visit conducted outside of scheduled visit window
- Device not used per labeling

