9.17.1 Study Exit

A study exit eCRF is required for all subjects. Prior to exiting a subject from the study, it is recommended to follow the subject until all ongoing system and/or procedure related AEs are resolved or unresolved with no further actions planned. Following exit, subjects will continue to receive standard medical care. Upon exiting from the study, no further study data will be collected or study visits will occur for the subject. All data available through the time of the subject's exit will be used for analysis.

Subjects are urged to remain in the study as long as possible but may be exited from the study for any of the following situations:

- Study completed
- Subject lost to follow-up

Medtronic Business Restricted

- Subject death
- Subject did not meet inclusion/exclusion criteria
- Investigator chose not to use the Novapak Nasal Sinus Packing and Stent device
- Subject did not provide consent (or data use protection authorization where required)
- Subject chooses to withdraw (e.g., consent withdrawal, relocation to another geographic location)
- Investigator deems withdrawal necessary (e.g., medically justified, inclusion/exclusion criteria not met, failure of subject to maintain adequate study compliance)

The following information is required to be collected at study exit:

- Date of Study Exit
- Reason for exit (subject status)
 - AE related
 - Covid related

If discontinuation is because of safety or lack of effectiveness, the subject shall be asked to be followed for collecting safety data outside the clinical investigation.

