13.1 General Aspects of Analysis

Novapak Nasal Sinus Packing and Stent Study is a prospective, non-randomized, non-blinded, multi-site, investigational, clinical study.

Medtronic Business Restricted

The statistical analyses will be performed by Medtronic employed statisticians. The study population is defined as all eligible patients who signed the Patient Informed Consent Form.

All data collected from enrolled subjects will be utilized in the analyses as appropriate. Analyses of the primary and secondary endpoints will be descriptive.

All continuous variables will be summarized as the number of subjects, means, standard deviations, medians, minimums, maximums, and interquartile ranges. Categorical variables will be summarized as frequencies and percentages.

Any deviations from the original statistical plan will be summarized in the Clinical Study Report(s) (CSRs), along with the justification for the deviations.

No statistical techniques will be used to impute missing data for continuous or categorical outcomes. If a subject's data are missing for any reason, that subject will not be included in that portion of the analysis. The number of subjects included in each analysis will be reported so that the reader can assess the potential impact of missing data.

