# 7.4 Handling of Missing, Unused, and Spurious Data and Dropouts

The analysis will be based on all observed data. No statistical techniques will be used to impute missing data for continuous or categorical outcomes. If a subject's data are missing for any reason, that subject will not be included in that portion of the analysis. The number of subjects included in each analysis will be reported so that the reader can assess the potential impact of missing data.

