## 7.9 Evaluation of Objectives

### 7.9.1 Safety objective assessment

The safety objective is evaluated by:

- The number of Adverse Events that are directly attributed to the device and/or those that cannot be determined.
- The number of Adverse Events.

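### The SAP's only analysis population leaves treated-but-ineligible subjects, and their adverse events, out of the primary safety summary, contrary to protocol sections 9.17.1 and 4.1.1.1.1

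*SAP*

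**What the plan says.** SAP section 7.1.3 gives a single definition: "The analysis population will include all patients that fulfill inclusion and exclusion criteria and use the Novapak Nasal Sinus Packing and Stent device". It sets two conditions, eligibility and device use. SAP section 7.9.1 evaluates the safety objective by two counts, the first being "The number of Adverse Events that are directly attributed to the device and/or those that cannot be determined" and the second all adverse events. It names no separate population. SAP section 3 ties any reported objective to this text: "the analysis of that objective will be performed as described in this SAP".

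The protocol foresees enrolment of ineligible subjects. Section 9.16 lists "Inclusion/exclusion criteria not met" as an example of a deviation, and section 9.17.1 lists the same event among the reasons for study exit. Of exited subjects in general, section 9.17.1 states: "All data available through the time of the subject's exit will be used for analysis". Section 4.1.1.1.1, which defines the primary safety endpoint as a rate with a confidence interval, has adverse events collected for each subject from treatment to study completion and sets no eligibility condition.

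Protocol section 13.1 says two things. Its population sentence reads "The study population is defined as all eligible patients who signed the Patient Informed Consent Form". The next paragraph reads "All data collected from enrolled subjects will be utilized in the analyses as appropriate".

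**The concern.** Safety is the primary objective, and the study is meant to support a CE Mark submission. A safety summary is normally expected to cover everyone exposed to the device. Here exposure is not enough: the subject must also have met the entry criteria.

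Those criteria are not neutral for this endpoint. Protocol section 10.2 explains that shellfish-allergy screening is there to reduce hypersensitivity to the chitosan in the device. The complaint record in section 10.1 includes one irritation report with potential shellfish hypersensitivity. Under section 9.4, a candidate with unknown allergy status may be included on the investigator's assessment, so a misjudged enrolment is plausible. If such a subject reacted to the device and was then classed as ineligible, SAP section 7.1.3 would remove the reaction from the primary summary. SAP section 7.1.2 would still show the deviation and subject counts, but not the event.

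**Working it through.** **Step 1: who is covered by which rule.** The plan states no figure to reproduce, so the first check sets the texts side by side.

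| Consented subject | SAP 7.1.3 | Protocol 13.1 study population | Protocol 9.17.1 data rule |
|---|---|---|---|
| Eligible, treated | in | in | used |
| Ineligible, treated | **out** | out | **used through exit** |
| Eligible, not treated | out | in | used through exit |
| Ineligible, not treated | out | out | used through exit |

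The second row is the conflict. The third row shows that protocol 13.1 and the SAP also differ on device use, so the documents do not settle the denominator of the safety rate.

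**Step 2: protocol 13.1.** Its population sentence requires eligibility, so on that condition it agrees with the SAP. Its all-data sentence points the other way, but it carries a qualifier and depends on the meaning of enrolled. Section 9.7 counts a subject as enrolled once consent is finalized, whereas the closing list in section 8.2 also requires that the eligibility criteria be met. Under 9.7 the sentence covers treated-but-ineligible subjects; under 8.2 it does not.

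**Step 3: size.** The documents give no number of ineligible treated subjects, no expected event rate and no confidence level. I assume 75 treated subjects (the minimum enrolment), subjects with at least one event as the unit, and exact two-sided 95% limits: lower = Beta quantile(0.025; x, n − x + 1), upper = Beta quantile(0.975; x + 1, n − x). For x = 0 the lower limit is 0 and the upper is 1 − 0.025^(1/n).

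*Illustration A: five subjects with events, three treated subjects excluded as ineligible.*
- All treated: 5/75 = 6.7% (2.2 to 14.9%).
- None of the five excluded: 5/72 = 6.9% (2.3 to 15.5%), a rise of 0.3 points.
- One of the five excluded: 4/72 = 5.6% (1.5 to 13.6%), a fall of 1.1 points.

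If ineligibility is unrelated to events, the number of event subjects among the three excluded is hypergeometric:
- P(0) = C(70,3)/C(75,3) = 54,740/67,525 = 0.811
- P(1) = 5 × C(70,2)/C(75,3) = 12,075/67,525 = 0.179
- P(2 or 3) = (700 + 10)/67,525 = 0.011

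*Illustration B: one subject with an event, one treated subject excluded.*
- All treated: 1/75 = 1.3% (0.03 to 7.2%).
- The excluded subject had the event: 0/74 = 0%, upper limit 1 − 0.025^(1/74) = 4.9%.
- By chance alone this has probability 1/75 = 1.3%. It becomes likely only if the event is linked to the unmet criterion, as with a shellfish reaction.

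**The case against.** Several points on the other side have weight.

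- *Section 9.17.1 is about study exit.* Its sentence can be read as a rule on which data are kept once follow-up stops, and it names no analysis set. Some subjects who exit as ineligible will never have been treated. Both points narrow the conflict, but they do not remove it: the sentence speaks of use in analysis, and ineligibility is on the same section's list of exit reasons.
- *SAP section 7.4 says "The analysis will be based on all observed data".* That is a missing-data rule. It creates no population and does not relax section 7.1.3.
- *The event would not vanish.* This stands. Protocol section 11 collects and reports adverse events with no eligibility condition, and section 15.9.2 requires deviations to appear in the final report. A reader might infer that such events would go unreported; the documents do not support that. What is lost is their place in the primary summary.
- *A reader might infer that protocol 13.1 flatly contradicts the SAP.* It does not, for the reasons in step 2 of the working.
- *A reader might infer that the SAP rule flatters the device.* Illustration A shows otherwise: when ineligibility is unrelated to events, the SAP rule most often raises the rate slightly.
- *Taken literally, section 9.17.1 covers untreated subjects too.* This also stands. The exit list includes the investigator's decision not to use Novapak, and section 9.7 asks for adverse events to be reported once consent is obtained. A treated-only set is therefore a sensible choice for a device rate rather than something the protocol text dictates, and adverse events in untreated subjects still need a place in the report.

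**Conclusion.** The point holds. As written, SAP section 7.1.3 removes treated-but-ineligible subjects and their adverse events from the primary safety summary, against protocol sections 9.17.1 and 4.1.1.1.1. Protocol 13.1 does not resolve the matter.

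The consequence is limited. The study has no hypothesis or performance goal, so no pass/fail decision turns on this. SAP section 7.9.1 asks only for counts; the rate and interval that would be affected are those of protocol section 4.1.1.1.1. On the assumed counts the shift is between a rise of about 0.3 points and a fall of about 1.3 points, with heavily overlapping intervals. It matters most when device-related events are rare and linked to an unmet criterion, because one exclusion can then turn a reported event into zero. All event and exclusion counts are assumptions. The inconsistency itself rests on the text alone and should be corrected before analysis.

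**What to change.** - In SAP section 7.1.3, define a safety set of all subjects in whom Novapak was used, regardless of eligibility or deviations. Use it for both numerator and denominator of the two adverse-event endpoints in SAP section 7.9.1.
- Keep eligible-and-treated as the effectiveness set.
- List any adverse events in consented-but-untreated subjects, whom protocol section 8.1 anticipates, separately and outside the device rate.
- Align the population wording in protocol section 13.1 with these sets, and reconcile the enrolment definitions in sections 8.2 and 9.7.

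The cost is a few sentences in each document and a little more analysis work. Device use, deviations and adverse events are already collected. The reported rate may move slightly in either direction.

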### 7.2 General Methodology

Categorical variables will be summarized with frequencies and percentages.

Summaries of continuous variables will include the sample size, mean and standard deviation. Additional summaries of the number with missing data, minimum, median, maximum, or sum may be presented as appropriate.

Statistical inferences will be performed as needed. For continuous variables, t-test, ANOVA, or nonparametric Wilcoxon test will be used; for categorical variables, Chi-square test or Fisher's exact test will be used.

## 7.3 Center Pooling

Data from all study centers will be pooled for the analysis. Descriptive summary may be provided by study center. If substantial center heterogeneity is present, exploratory analysis may be performed to help understand the variations.

# 7.4 Handling of Missing, Unused, and Spurious Data and Dropouts

The analysis will be based on all observed data. No statistical techniques will be used to impute missing data for continuous or categorical outcomes. If a subject's data are missing for any reason, that subject will not be included in that portion of the analysis. The number of subjects included in each analysis will be reported so that the reader can assess the potential impact of missing data.

## 7.5 Adjustments for Multiple Comparisons

No adjustments for multiple comparisons will be made.

## **7.6** Demographic and Other Baseline Characteristics

### 7.6.1 Demographics

Demographics will be summarized in descriptive tables, including but not limited to:

- Age at consent (in years)
- Gender
- Race
- Ethnicity

### 7.6.2 Baseline Characteristics

Baseline characteristics will be summarized in descriptive tables, including but not limited to:

• Surgical history

#### 7.6.3 Baseline Assessment

Baseline assessments will be summarized using descriptive statistics for patients with scores as follows:

- SNOT-22 score
- Lund-Mackay score
- Lund-Kennedy score

## 7.7 Treatment Characteristics

Treatment characteristics will be summarized in descriptive tables, including but not limited to:

- Surgical location (left, right, or both nasal cavities)
- Model (CS3600, CS3900)

### 7.8 Interim Analyses

No interim analyses are planned for this study.

## 7.9 Evaluation of Objectives

### 7.9.1 Safety objective assessment

The safety objective is evaluated by:

- The number of Adverse Events that are directly attributed to the device and/or those that cannot be determined.
- The number of Adverse Events.

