4.1.1.1.1 Primary Device Safety Endpoints

The primary safety endpoint is an assessment of all AEs that are directly attributable to the device and/or for which cause cannot be determined, and that meet the definition of designated primary safety endpoint AEs (see section 11.4) that will be used to determine the point estimate and its confidence interval. This endpoint will be analyzed by calculating the point estimate with a confidence interval of its rate. All AEs will be collected for each subject from time of treatment until their study completion.

Study completion for each subject is the time point at which the 30-day follow-up visit is completed, outstanding AE follow-up (if any) has been concluded, and a Study Exit CRF has been completed. For subjects who withdrew or were lost to follow-up, study completion will be the date of withdrawal or the date the subject meets the definition of lost to follow-up. Refer to **Section 13** for how missing data will be handled.

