	
• the event is not a known complication or side effect of the procedures, study device or product category the device belongs to or of similar devices• the event has no temporal relationship with the use of the study device or the procedures• the event does not follow a known response pattern to the study device (if the response pattern is previously known) and is biologically implausible• the discontinuation of study device application or the reduction of the level of activation/exposure - when clinically feasible – and reintroduction of its use (or increase of the level of activation/exposure), do not impact on the event• the event involves a body-site, or an organ not expected to be affected by the device or procedure• the event can be attributed to another cause (e.g. an underlying or concurrent illness/ clinical condition, an effect of another device, drug, treatment or other risk factors)• harms to the subject are not clearly due to use error 
In order to establish the non-relatedness, not all the criteria listed above might be met at the same time, depending on the type of device/procedures and the seriousness of the event.

Relationship - Possible	The relationship with the procedure or use of the study device is weak but cannot be ruled out completely. Alternative causes are also possible (e.g. an underlying or concurrent illness/ clinical condition or/and an effect of another device, drug or treatment). Cases where relatedness cannot be assessed, or no information has been obtained should also be classified as possible.
Relationship - Probable	The relationship with the procedure or use of the study device seems relevant and/or the event cannot reasonably be explained by another cause, but additional information may be obtained.

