11.5 Reporting of Adverse Events

11.5.1 Adverse Event and Device Deficiency Classification

All AE and DD will be reviewed by a Medtronic representative. AEs will be classified according to the definitions provided.

Upon receipt of AE at Medtronic, a Medtronic representative will review the AE/DD for completeness and accuracy and when necessary, will request clarification and/or additional information from the Investigator. Medtronic will utilize Medical Dictionary for Regulatory Activities (MedDRA), to assign a MedDRA term for each AE based on the information provided by the investigator.

Regulatory reporting of AEs and DDs will be completed according to local regulatory requirements. Refer to **Table 11** for a list of required investigator and Medtronic reporting requirements and timeframes. It is the responsibility of both to abide by any additional AE reporting requirements stipulated by the IRB/REB responsible for oversight of the study.

Medtronic Business Restricted

Appendix A contains the FAL, which is a list of AEs related to the device or procedure that have been observed in previous studies and may be experienced by subjects. This list may help to assess if an AE is unanticipated in nature.

For emergency contact regarding a SAE and/or SADE, contact a study representative immediately (refer to the study contact list provided in the study site's study documents binder/investigator site file or refer to the Sponsor contact information provided on the title page).

AEs will be classified according to the standard definitions as outlined below:

Table 10: Adverse Event Classification Responsibilities

What is classified?	Who classifies?	Classification Parameters
Relatedness	Investigator	Device and/or Procedure. 
Relationship: not related, possible, probable, causal
	Sponsor	Device and/or Procedure. 
Relationship: not related, possible, probable, causal
Seriousness	Investigator	SAE, DD with SADE potential
	Sponsor	SAE, DD with SADE potential
Diagnosis	Investigator	Based on presenting signs and symptoms and other supporting data
	Sponsor	MedDRA term assigned based on the data provided by Investigator

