12.1 Clinical Events Committee Review

CEC is not needed for this study. This decision was made based on the following criteria: fast enrollment in this trial makes a CEC impractical, and there are no additional benefits of a CEC reviewing the data.

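### The primary device-AE endpoint is worded in causality terms that the recorded four-level relatedness scale does not contain, and no rule says whose rating counts

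*SAP*

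**What the plan says.** **Endpoint.** SAP 7.9.1 lists "The number of Adverse Events that are directly attributed to the device and/or those that cannot be determined" and, separately, the number of all AEs. Protocol 4.1.1.1.1 describes the primary endpoint as an assessment of "all AEs that are directly attributable to the device and/or for which cause cannot be determined", restricted to events "that meet the definition of designated primary safety endpoint AEs (see section 11.4"), and promises a point estimate with a confidence interval for the rate. Protocol 13.3 repeats the two classes without that restriction, and the SAP does not mention it.

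**What is recorded.** Protocol 11.5.1, Table 10, gives the scale as "Relationship: not related, possible, probable, causal", for device and/or procedure. It lists the investigator and the sponsor as separate classifiers of relatedness on that scale.

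**Level definitions (protocol 11.4, Table 9).**
- *Possible*: "The relationship with the procedure or use of the study device is weak but cannot be ruled out completely". The entry adds: "Cases where relatedness cannot be assessed, or no information has been obtained should also be classified as possible".
- *Probable*: the relationship "seems relevant and/or the event cannot reasonably be explained by another cause".
- *Causal*: association beyond reasonable doubt.

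**Adjudication.** Protocol 12.1: "CEC is not needed for this study". Protocol 13.1 describes the study as non-blinded and has statisticians employed by the sponsor perform the analyses.

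**The concern.** The endpoint and the data use two different vocabularies, and neither document links them. An analyst therefore has to decide which recorded levels stand for *directly attributed* and *cannot be determined*, and which of two ratings to use where they differ. Several choices comply with the text, and they can be made once the events are known.

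At stake is the main safety figure of an unmasked single-arm study meant to support a CE-mark submission (protocol 3.2). The protocol promises a rate with an interval, so the numerator is the result. Two competent analysts working from the same database could report different primary rates, each with a fair claim to have followed the plan.

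**Working it through.** **1. Map the endpoint terms to the recorded levels.**

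| Recorded level (protocol 11.4) | *Directly attributed*? | *Cannot be determined*? |
|---|---|---|
| Causal | Nearest match | No |
| Probable | Not named; depends on the reader | No: a cause has been judged |
| Possible, weak link that was assessed | No | Arguable: not excluded, but assessed |
| Possible, unassessable or no information | No | Yes |
| Not related | No | No |

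The third and fourth rows share one code. A rule that counts unassessable events but not weak links cannot be applied from the level alone. If *directly attributed* is equated with *causal*, probable events fall into neither class, although they carry more evidence of a device link than the unassessable events that do count.

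**2. Look for a rule that settles it.** Protocol 4.1.1.1.1 refers to 11.4 for the designated events, but Table 9 has no such entry. Protocol 9.15 allows the AE form to serve as source for relatedness but does not say whose rating is analysed. Table 10 sets no precedence between the two assessors. The bias measures in protocol 13.6 cover eligibility review and standardised data acquisition, not relatedness. No rule was found.

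**3. Illustrate the size.** The plan contains no figure to reproduce: there is no expected event rate, and the minimum of 75 subjects was not derived statistically (SAP 6).

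Inputs: n = 75 from the plan. Assumed: all 75 analysed, one event per subject, a two-sided 95% level (the plan gives neither level nor method), and a mix of 2 causal, 3 probable, 3 weak-possible and 1 unassessable.

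Exact (Clopper-Pearson) limits for x events: lower = 2.5% quantile of Beta(x, n − x + 1); upper = 97.5% quantile of Beta(x + 1, n − x).

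| Reading | x | x/75 | Exact 95% CI |
|---|---|---|---|
| Literal: causal + unassessable | 2 + 1 = 3 | 4.0% | 0.8-11.2 |
| Causal + probable + unassessable | 2 + 3 + 1 = 6 | 8.0% | 3.0-16.6 |
| Possible or higher | 2 + 3 + 3 + 1 = 9 | 12.0% | 5.6-21.6 |

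Only the last row can be computed from the recorded levels; the first two need *possible* to be split.

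Other assumed mixes, comparing the literal reading with possible or higher:
- 1 causal, 3 probable, 3 weak-possible, 1 unassessable: 2/75 = 2.7% (0.3-9.3) against 8/75 = 10.7% (4.7-19.9).
- 0 causal, 3 probable, 3 weak-possible, 0 unassessable: 0/75 (0-4.8) against 6/75 = 8.0% (3.0-16.6).

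The choice of assessor works in the same way: each event re-rated across the cut moves the rate by 1/75 = 1.3 percentage points.

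**The case against.** The best defence is that the wording has a sensible reading: everything not ruled out counts, which means possible, probable and causal. Dropping probable events requires equating *directly attributed* with the beyond-reasonable-doubt standard, and no section does so. The analyses are descriptive, with no hypothesis or success threshold (protocol 13.1, 13.5). All AEs are tabulated as well, so a collected event re-rated as not related still appears there. The event mixes above are invented.

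Much of this stands, and it rules out several stronger inferences a reader might draw:
- *That the endpoint could be reported as causal events only.* It could not; both documents add events of undetermined cause, which reach into *possible*.
- *That probable events will be lost, or that the sponsor's rating prevails.* The text permits either but states neither.
- *That recent surgery, as another cause, lets device events be classed as not related.* The *possible* entry expressly allows alternative causes, and procedure relatedness is rated on its own axis.
- *That device and procedure relatedness are merged.* Table 9 defines them separately and Table 10 rates both. The case report form is not among the documents, so it may also hold a field that identifies unassessable events.

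The defence does not supply the missing rule. The inclusive reading is sensible but unwritten, and a descriptive rate still needs a defined numerator.

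**Conclusion.** The point holds as a defect in how the primary endpoint is specified. As worded, the numerator cannot be formed from the recorded relatedness levels. Its literal reading orders the evidence wrongly. The governing assessor is unstated, and the definition the protocol cites is absent from section 11.4.

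The size is unknown. In the three assumed mixes the inclusive rate was three to four times the literal one (9/3 = 3; 8/2 = 4), or 8.0% against zero where no event was causal or unassessable. These figures show sensitivity to the choice of levels; they do not forecast this study's rate, and they depend on 75 analysed subjects with one event each.

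This is a should-fix. With no threshold to pass and all AEs also reported, the gap makes the primary device-AE rate irreproducible, but it does not show that the result will be biased towards the device.

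**What to change.** 1. In protocol 4.1.1.1.1 and 13.3 and in SAP 7.9.1, define the numerator as AEs whose relationship to the **device** is rated possible, probable or causal, in place of the two undefined classes. Bring the synopsis into line.
2. Prespecify which rating governs. The higher of the investigator's and the sponsor's is one workable rule; another is acceptable if fixed before the data are analysed.
3. Tabulate events by relatedness level and by assessor, and list every discordant event.
4. Define the designated primary safety endpoint AEs in section 11.4 and carry the restriction into the SAP, or delete it.

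Cost: wording changes in two documents, one extra table and a listing. Table 10 already requires both ratings, so no new assessments are needed. The downside is that the reported device-AE rate may be somewhat higher than under a narrower reading.
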